- **Data Analysis:** Descriptive statistics will be used for all objectives, and no hypothesis testing will be conducted. Incidence and prevalence calculations will be conducted.

- **Milestones:** The study will be registered in the HMA-EMA Catalogues of RWD studies on July 14, 2025, followed with data collection commencing on July 15, 2025. An interim study analysis is scheduled for release on September 30, 2025. Data collection will conclude on June 30, 2026, followed by the final study report on November 30, 2026.

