9. RESEARCH METHODS

9.1. Study Design

This retrospective cohort study will assess the demographics, clinical history, SUD process, HCRU, and safety of elranatamab in MM patients with an elranatamab hospital claim. De-identified data from the Japan Medical Data Vision (MDV) will be used.

[figure not shown]
A retrospective cohort design was chosen because it allows for efficient use of existing RW data to evaluate treatment patterns and outcomes in a newly approved therapy, without the need for prospective data collection. This design is well-suited for descriptive analyses and enables timely insights into the early use of elranatamab in a RW setting.

The primary endpoints include patient demographics, clinical characteristics, and treatment patterns. Secondary endpoints include HCRU and safety outcomes. No formal measures of effect will be calculated. All analysis will be descriptive, with no a priori hypotheses or statistical comparisons between exposure groups.

The study population will be comprised of individuals aged 18 and older who initiated elranatamab between March 26, 2024, the PMDA approval date for elranatamab, and the end of data availability. The study period will be from the start of data availability, April 2008, to the end of data availability in MDV. The study period will remain the same for all study objectives. The patient baseline period will be from MM diagnosis to the start of the index treatment. The patient index date will be determined as the date of first hospital claim with an administration of elranatamab. The follow-up period will be defined as the period between the index date and the end of the hospital claim of the last elranatamab administration

inclusive. The SUD period will be defined as the period between the date of the first 44mg/1.1mL vial and the first 76mg/1.9mL vial of elranatamab, see more details in Section 9.2 and 9.3.1. Figure 1

Figure 1. Study design

Abbreviations: CCI: Charlson Comorbidity Index; HCRU: Health Care Resource Utilization; MM: multiple myeloma; SUD: Step-up dosing;

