SUD period: defined as the period between a patient's first 44mg/1.1mL vial of elranatamab and first 76mg/1.9mL vial of elranatamab, inclusive. See Section 9.3.1 and Annex 1 for more details. Within the SUD period, three sub-periods are identified:

- **Overall:** defined as the period between first 44mg/1.1mL vial and first 76mg/1.9mL vial of elranatamab.
- **First 44mg/1.1mL vial – Second 44mg/1.1mL vial:** defined as the period between the two 44mg/1.1mL vials of elranatamab, if second 44mg/1.1mL vial is administered.
- **Second 44mg/1.1mL vial – first 76mg/1.9mL vial:** defined as the period between the second 44mg/1.1mL vial and the first 76mg/1.9mL vial of elranatamab, if second 44mg/1.1mL vial is administered.

Follow-up period: defined as the period between the first hospital claim for elranatamab (index date) and the end of the hospital claim of the last elranatamab administration. Within this follow-up period, five sub-periods are identified (when sufficient follow-up time is available at the patient level). These sub-periods allow for reporting study endpoints across different phases of the follow-up period, and are based on expected dosing administrations and schedule of patients with switch to bi-weekly administrations from label guidance (see [Table 10. Dosing Schedule of Elranatamab during Follow-up Period for Patients Switching to](#)

[Q2W](#) and [Table 11. Dosing Schedule of Elranatamab during Follow-up Period for Patients staying on QW](#)):

- **Index date to day 8:** defined as the first 8 days post-index date, inclusive. Also defined as day 1 to day 8.
- **Day 9 to day 168:** defined as the period from day 9 to day 168 post-index date.
- **Day 169+:** defined as the period from day 169 post-index date to end of follow-up period.

- **Overall follow-up:** defined as the period from index date to end of follow-up period.

IVIG follow-up assessment period: defined as the 30-day window post index date. If a patient has fewer than 30 days of data available post to the index date, the assessment window will be equal to the maximum number of days available post to the index date.

CRS/ICANS follow-up assessment period: defined as the 14-day window post index date. If a patient has fewer than 14 days of data available post to the index date, the assessment window will be equal to the maximum number of days available post to the index date.

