Days from index to first ICANS event	Outcome	MDV	Time in days from index date to first ICANS event (continuous)	CRS/ICANS follow-up assessment period
Cytopenia occurrence ¹	Outcome	MDV	Disease code or labs value for cytopenias occurrences (Yes/No): 
 Anemia Leukopenia Lymphopenia Neutropenia Thrombocytopenia Number and proportion of patients with a health claim code for each cytopenia will also be reported. Incidence and prevalence will be reported, see Section 9.7.2 for additional details.	SUD period
Days from index to first cytopenia	Outcome	MDV	Time in days from index date to first cytopenia (continuous)	SUD period

090177e1a4a71ff1\Approved\Approved On: 05-Nov-2025 14:15 (GMT)

Abbreviations: CRS: cytokine release syndrome; ICANS: Immune effector Cell Associated Neurotoxicity Syndrome; SUD: step-up dosing.

Notes:

1. Variable will be measured as incident and prevalent. Incident cases have a 30-day washout period applied.

Table 8. Variables for Outcomes (Objective 6 - Infections)

Variable	Role	Data Source	Operational Definition	
			Definition	Assessment Period(s)
Infection occurrences ¹	Outcome	MDV	Disease code for infections; the list of infections of interest will be outlined in the SAP (Yes/No) Incidence and prevalence will be reported, see Section 9.7.2 for additional details.	Follow-up period
Days from index to infection	Outcome	MDV	Time in days from index date to first infection (continuous)	Follow-up period
Days between infections	Outcome	MDV	Days between infection claims (continuous) For patients with ≥ 2 disease code for infections listed in the SAP during the time period	Follow-up period

Variable	Role	Data Source	Operational Definition	
			Definition	Assessment Period(s)
Antibiotics	Outcome	MDV	Health claim code for antibiotic treatment (Yes/No)	Follow-up period
Antivirals	Outcome	MDV	Health claim code for antiviral treatment (Yes/No)	Follow-up period
Antifungals	Outcome	MDV	Health claim code for antifungal treatment (Yes/No)	Follow-up period

Notes:

1. Variable will be measured as incident and prevalent. Incident cases have a 60-day washout period applied.

Table 9. Variables for Outcomes (Exploratory Objective 1 – Supportive Medications)

Variable	Role	Data Source	Operational Definition	
			Definition	Assessment Period(s)
Dexamethasone	Outcome	MDV	Health claim code for dexamethasone (Yes/No)	SUD period
Diphenhydramine	Outcome	MDV	Health claim code for diphenhydramine (Yes/No)	SUD period

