9.5. Study Size

The study sample will be identified from secondary data from Japanese hospitals that has already been collected. As the MDV database does not include all Japanese hospitals, the sample will be a convenience sample. The most recent data cut available from MDV will be used for the report. All patients who meet the inclusion/exclusion criteria defined in [Section 9.2](#) will be included in the analyses.

This is a descriptive study with no a priori hypotheses; therefore, formal sample size calculations are not applicable. However, to provide an indication of the expected sample size, the February 2025 data cut, MDV included 128 patients that had at least one hospital claim for elranatamab.

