9.7. Data Analysis

All analysis will be descriptive in nature and no formal statistical comparisons will be performed between groups. All characteristics and endpoints will be reported separately for each assessment period and patient exposure groups of interest as defined in [Table 2. Patient Exposure Groups Stratification and Assessment Period for Study Objectives](#).

Raw data transferred by MDV will be reviewed for completeness, consistency and plausibility. Records with missing or implausible values (e.g., negative age, invalid dates) will be flagged and addressed according to predefined rules in the SAP. Duplicate records will be identified and removed. Variables will be derived and categorized as needed for analysis. Diagnosis and procedure codes will be mapped to standardized categories using the International Classification of Diseases, 10th revision (ICD-10) and Healthcare Common Procedure Coding System (HCPCS) classification systems. Missing data will be reported, and no imputation will be performed unless otherwise specified in the SAP.

Detailed methodology for summary and statistical analyses of data collected in this study will be documented in a SAP, which will be dated, filed, and maintained by the sponsor. The SAP may modify the plans outlined in the protocol; any major modifications of primary endpoint definitions or their analyses would be reflected in a protocol amendment.

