9.7.1. Descriptive Analysis

Dichotomous and categorical variables will be summarized by the number and percentage of patients in each category. Continuous variables will be described using mean, standard deviation (SD), median, interquartile range (IQR), minimum, and maximum. If applicable, the frequency and percentage of patients with missing data for each variable will be described. For reporting conventions, mean, median, and SD will be rounded to 1 decimal place. Percentages will be rounded to 1 decimal place.

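### Days from index to infection is a plain mean and median that only infected patients can enter, so it leans towards early infections and drifts with the data cut

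*Protocol*

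**What the plan says.** - **Variable.** Protocol Table 8 (under the heading 1.1.2, Covariates and Outcomes) gives days from index to infection as "Time in days from index date to first infection (continuous", assessed over the follow-up period. The next row, days between infections, states its restricted population (two or more infection codes). This row states none.
- **Summary.** Section 9.7.1: "Continuous variables will be described using mean, standard deviation (SD), median, interquartile range (IQR), minimum, and maximum".
- **Patients without a value.** Section 9.7: "Missing data will be reported, and no imputation will be performed unless otherwise specified in the SAP".
- **Observation window.** Section 9.2 defines follow-up as "the period between the first hospital claim for elranatamab (index date) and the end of the hospital claim of the last elranatamab administration".
- **Entry.** Section 9.1 admits patients who "initiated elranatamab between March 26, 2024, the PMDA approval date for elranatamab, and the end of data availability".
- **Timing.** The Milestones section plans an interim analysis for 30 September 2025. The Abstract says "Data collection will conclude on June 30, 2026". Section 12 plans to disseminate both interim and final results.
- **Related measures.** Table 2 assigns Objective 6 to the index date, days 1 to 8, days 9 to 168, day 169 onwards and the overall period. Section 9.7.2 gives incidence and prevalence of infection.

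The protocol names no censoring rule, Kaplan-Meier estimate or cumulative incidence method, and section 9.7.6 plans no sensitivity analysis.

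**The concern.** Time to first infection is a time-to-event quantity, but it is set up as an ordinary measurement. A patient who reaches the end of follow-up without an infection has no date and so no value. At best that patient appears in a missing count. The mean and median then describe only infections that came early enough to fall inside each patient's own window, and someone who started shortly before the data cut can contribute only a short time or nothing.

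CRS and ICANS have a 14-day window and cytopenia is confined to the step-up period. Infection is the time-to-first-event row that runs over open-ended follow-up, so the effect matters most here. The Abstract lists time from index to infection among the study outcomes. An unlabelled median would be read as when infections occur in patients given elranatamab, and it would move between the interim and final results with no change in risk.

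This is more than detail left to the SAP, because the protocol itself fixes both the variable type and the summary statistics.

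**Working it through.** The protocol states no expected time to infection or time on drug, so there is no figure of its own to reproduce. The direction follows from the definitions. The size needs assumptions.

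**Inputs from the protocol**
- First possible entry: 26 March 2024.
- Interim analysis, 30 September 2025: 553 days after first entry.
- End of data collection, 30 June 2026: 826 days after first entry.
- Indicative count at the February 2025 data cut: "MDV included 128 patients that had at least one hospital claim for elranatamab". Taking the end of that month gives 339 days.

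**Assumed inputs**
- Latent time to first infection is exponential with median m = 60, 120 or 240 days.
- Time on drug is exponential with median 150 days, independent of infection.
- Entry is uniform over the span c, and data run right up to the cut date.

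**Step 1: complete on-treatment follow-up, no data cut.** With λ = ln 2 / m, μ = ln 2 / 150 and k = λ + μ, the median among patients infected on treatment is ln 2 / k = 1 / (1/m + 1/150).
- m = 60: 43 days
- m = 120: 67 days
- m = 240: 92 days

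**Step 2: add the data cut.** An infection at day t is seen only if the patient is still on drug and entered at least t days before the cut. The observed share by day t is

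F(t) = λ × [ (1 − e^(−kt))/k − (1 − e^(−kt)(1 + kt))/(c k²) ],

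and the infected-only median solves F(t) = F(c)/2. For m = 120, k = 0.01040. At c = 826, F(c) = 0.491 and F(58.6) = 0.245, so the median is about 59 days and 51% of patients have no value.

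| Latent median | No data cut | Cut at 553 days | Cut at 826 days |
|---|---|---|---|
| 60 | 43 | 38 | 40 |
| 120 | 67 | 55 | 59 |
| 240 | 92 | 69 | 77 |

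**Step 3: split the gap (m = 120).**
- From 120 to 67 days: 53 days, due to the on-treatment window.
- From 67 to 59 days: 8 days (8/67 = 12%), due to the data cut at the final analysis.
- From 67 to 55 days: 12 days (12/67 = 18%), due to the cut at the interim date.
- Drift from interim to final: 59 − 55 = 4 days.

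**Step 4: check the alternative.** In a simulation of 400,000 patients per scenario, with exponential times, latent medians of 60 to 365 days and median time on drug of 60, 120 or 240 days, Kaplan-Meier on all patients censored at end of follow-up returned the latent median to within about 2% wherever it was reached. With a latent median of 365 days and a 339-day span it was correctly not reached. Infected-only medians were below the latent value in every scenario. Death was not modelled separately.

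**The case against.** **Infection-free patients are not lost from Objective 6.** Infection yes/no, incidence and prevalence are reported by sub-period with those patients in the denominator, which also shows coarse timing. This stands. A reader might infer that the infection results as a whole leave them out, and the protocol does not support that. These measures nevertheless do not correct the days-to-infection row.

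**Onset time among affected patients is a legitimate description.** It is, if labelled, and here it is not. A label alone would also leave the dependence on the data cut (55 or 59 days against 67).

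**The distortion is easily overstated.** This stands too. A reader might set 59 days against a latent 120 and conclude that the data cut halves the estimate. Most of that gap is the on-treatment window the protocol chose. A reader might also treat February 2025 as the interim and infer a shift from 47 to 59 days. February 2025 is only the date of the feasibility count, and the planned interim date gives a shift of about 4 days. A data extract earlier than that date would widen it somewhat.

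**Treating end of treatment as a competing event answers a different question and cannot be run as the protocol stands.** Correct. With m = 120 that curve levels off at 150/270 = 56% and crosses 50% only at about 221 days (ln 10 / k), so it does not recover 120. Follow-up ends at the last claim for everyone, and no rule separates stopping from the data cut.

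**The study is descriptive and Objective 6 is secondary.** True, and this limits the weight of the point.

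**Conclusion.** The point holds in a limited form. As fixed by Table 8 and section 9.7.1, the days-to-infection summary is conditional on an observed infection without saying so, leans towards early infections, and depends on how long patients were observed. The direction is secure given patient-specific follow-up and staggered entry. The size cannot be derived from the protocol. In the 120-day example, the data cut alone takes the median from 67 to about 55 days at the interim date and 59 at the final date. Across latent medians of 60 to 240 days, the final figure is about 3 to 15 days below the value with complete on-treatment follow-up (43 to 40; 92 to 77). These figures rest on constant hazards, independent stopping, uniform entry and 150 days' median time on drug. The change is worth making because this is a named outcome of a safety study and both interim and final results are to be published. It does not undermine the incidence and prevalence results.

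**What to change.** In Table 8 and section 9.7:

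1. Report time from index to first infection in the whole study population as a cumulative incidence curve (Aalen-Johansen) with numbers at risk, for example at days 8, 30, 90 and 168.
2. Censor infection-free patients at the protocol's own end of follow-up, "the end of the hospital claim of the last elranatamab administration". Treat death within follow-up as a competing event; section 9.4 lists mortality among the available data.
3. State that this is an on-treatment estimate and that censoring at the last claim may be informative. Treat stopping elranatamab as a competing event only if the SAP defines discontinuation.
4. Keep the mean and median, labelled as among patients with an infection, with the numbers infected and not infected.

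**Cost.** One further standard analysis in SAS, the planned software, from dates already held or derived, and short additions to the text. No new data are needed. The downside is imprecision at late times. Under the 120-day and 150-day assumptions with 128 patients and a 339-day entry span, the number at risk at day 168 is about 128 × e^(−0.01040 × 168) × (1 − 168/339) = 128 × 0.174 × 0.504 = 11. Intervals there would be wide, and showing the numbers at risk makes that plain.

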9.7.2. Incidence and prevalence calculations

The incidence of CRS, ICANS, and cytopenias will be determined by counting the number of new cases that arise within a specified time frame, divided by the population at risk during that period. An incident case is defined as a new occurrence of the condition following a 30-day washout period, during which no previous cases are considered. The prevalence of CRS, ICANS, and cytopenia will be calculated by counting the total number of cases (both new and existing) present in the population at a specific point in time, divided by the total population size.

Similarly, the incidence of infections will be calculated by counting the number of new cases that arise within a specified time frame, with a 60-day washout period applied to define new cases. The prevalence of infections will be calculated by counting the total number of infection cases present in the population at a specific point in time, divided by the total population size.

$$\text{Incidence Rate} = \frac{\text{Number of new cases}}{\text{Population at risk}} * \text{Population size}$$

$$\text{Prevalence Rate} = \frac{\text{Number of cases}}{\text{Total population}} * 100$$

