9.7.4. Healthcare Resource Utilization and Costs

All-cause HCRU will be measured as the total number IP, OP, and ED that occurred over the follow-up period. Health claims will only be counted once per day to estimate visits. Additionally, the total length of IP stays will be reported among patients with at least one IP visit. Costs will be adjusted for inflation. More details will be provided in the SAP.

PPPM

PPPM standardizes HCRU and cost by calculating the average of a specific variable or a number of specific events (e.g., ED health claims, IP health claims) per month for each patient. In this study, PPPM will be used to report ED, IP and OP visits and cost for the HCRU baseline period and the follow-up period. To obtain PPPM, the following formula will be used for each patient:

$$PPPM = \frac{\text{Total number of events during a specified period}}{\text{Duration of the specified period (in months)}}$$

PPPD

PPPD standardizes HCRU and cost by calculating the average of a specific variable or a number of specific events (e.g., ED health claims, IP health claims) per day for each patient. In this study, PPPD

090177e1a4a71ff1\Approved\Approved On: 05-Nov-2025 14:15 (GMT)

will be used to report ED, IP and OP visits and cost for the SUD period. To obtain PPPD, the following formula will be used for each patient:

$$PPPD = \frac{\text{Total number of events during a specified period}}{\text{Duration of the specified period (in days)}}$$

This calculation will allow meaningful comparisons across patients with varying assessment period lengths, by normalizing resources use to a monthly rate. Summary statistics (mean, median, min, max) will then be reported to understand average monthly cost and utilization patterns across patients.

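### Table 8 labels an outcome as time between infections but measures it between claims, so repeat coding of one infection counts as an interval between infections

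*Protocol*

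**What the plan says.** Protocol Table 8 (Section 1.1.2 as numbered, within Section 9.3) lists the infection outcomes of Objective 6. One row is named "Days between infections" and its definition reads "Days between infection claims (continuous". It applies to patients with two or more instances of a "disease code for infections listed in the SAP during the time period". The row gives no minimum gap, no onset date and no rule for joining codes that belong to one infection.

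The row for infection occurrences in the same table carries note 1, which says: "Incident cases have a 60-day washout period applied". Section 9.7.2 repeats this for the incidence calculation, "with a 60-day washout period applied to define new cases". The interval row does not carry note 1.

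What Table 8 hands to the SAP is the set of conditions: "the list of infections of interest will be outlined in the SAP (Yes/No". The unit of the interval, the claim, is fixed in the protocol itself.

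**The concern.** A hospital claims database records contacts and coded diagnoses, and one infection can be coded on several dates. If each code is a data point, the gaps between them reflect how often the hospital re-codes an open diagnosis as well as how often patients become infected again. The label tells the reader only the second.

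Infection is a secondary safety objective of a study designated as a PASS. The low-weight subgroup (Section 9.7.5) repeats it, and publication is planned (Section 12). A median of one or two weeks under this label would read as rapid recurrence when it might only show coding frequency. Table 4 avoids this for drug administration, where the row labels themselves say that the intervals are between claims.

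**Working it through.** The protocol states no figure for this outcome, so there is none to reproduce. The check has three parts.

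**1. Does another rule merge repeat codes?** Section 9.7 says "Duplicate records will be identified and removed". This deals with duplicate records, not with a later claim for the same infection. Section 9.7.4 says "Health claims will only be counted once per day to estimate visits". This is a rule for counting healthcare visits, and at most it would merge claims on one day. Codes on later days remain under both rules.

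**2. What does the written definition return?** Assume two infections starting D days apart, each coded k times at a spacing of g days. D, k and g are assumptions; the protocol gives none of them.

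- Number of claim intervals: 2k − 1.
- Sum of the intervals (from the earliest code to the latest): D + (k − 1)g.
- Mean interval: [D + (k − 1)g] / (2k − 1).
- Interval between onsets: D.

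For D = 120, g = 7 and k = 4, the claims fall on days 0, 7, 14, 21, 120, 127, 134 and 141. The gaps are 7, 7, 7, 99, 7, 7, 7. The mean is 141/7 = 20.1 days and the median is 7 days.

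The range over other assumed patterns is:

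| Assumed pattern | Claim gaps (days) | Mean | Median | Onset to onset |
|---|---|---|---|---|
| Two infections, D = 120, each coded once | 120 | 120 | 120 | 120 |
| D = 120, each coded twice, 7 days apart | 7, 113, 7 | 127/3 = 42.3 | 7 | 120 |
| D = 120, each coded weekly four times | 7, 7, 7, 99, 7, 7, 7 | 20.1 | 7 | 120 |
| D = 100, each coded twice, 14 days apart | 14, 86, 14 | 114/3 = 38 | 14 | 100 |
| D = 100, each coded weekly four times | 7, 7, 7, 79, 7, 7, 7 | 121/7 = 17.3 | 7 | 100 |
| One infection, coded weekly four times | 7, 7, 7 | 7 | 7 | none |
| One infection, coded three times, 30 days apart | 30, 30 | 30 | 30 | none |

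Without re-coding the two measures agree. In these patterns, one repeat code per infection is enough to pull the median down to the re-coding spacing. The last two rows show a single infection yielding intervals where none should exist.

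The last column treats a code as a new infection only after more than 60 days without an infection code. In the 120-day patterns the result is the same if the 60 days run from the previous onset.

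**3. What happens in the short sub-periods?** Table 2 assesses Objective 6 on the index date, from day 1 to day 8, from day 9 to day 168, from day 169 onward and overall. Some rows of Table 5 are limited to the overall period; this row of Table 8 is not. Within days 1 to 8 the largest possible gap is 8 − 1 = 7 days, and on the index date it can only be 0. Under a washout pooled over all infections, neither window could hold an interval between two new cases.

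**The case against.** The strongest reply is that the row says openly what it measures. A claim interval is a legitimate descriptive quantity, and note 1 is attached only to infection occurrences, and there only to incident cases. Nothing extends the washout to this row. That stands: a reader might infer that the protocol breaks its own 60-day rule, but no such rule is stated for this variable.

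Two further inferences are tempting and also fail. One is that every interval under 60 days is false. The protocol does not say whether the washout runs over all infections pooled or separately by type. If it runs by type, two different infections 20 days apart are both new cases and the short interval is real. The other is that the row contradicts the incidence results. Incidence counts new cases over a population at risk and this row gives days between claims, so different values are no contradiction.

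The SAP, which is not at hand, might add an episode rule, since Section 9.7 lets it modify the plan. However, the protocol already fixes the claim as the unit, so this is not a detail merely left open. The reply does not answer the remaining point: the label promises time between infections and the definition does not deliver it.

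**Conclusion.** The point holds as a mismatch between label and definition, and as an inconsistency within Objective 6 over what counts as a separate infection. Followed as written, the plan would report gaps between repeat codes of one infection as gaps between infections.

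The direction is clear, because extra codes for an infection add intervals that are not between infections and shorten the remaining ones. The size is not known. A reader might infer that intervals under 60 days will make up most of the distribution, but the protocol gives no re-coding frequency to support that. The table above shows anything from no distortion to a median of 7 days in place of 120, depending on the assumed pattern.

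The effect is confined to this descriptive row and to who qualifies for it. Incidence, prevalence and time to first infection do not depend on it. The row should be corrected before analysis, but it does not threaten the study's main results.

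**What to change.** Redefine the row as days between the onset dates of successive new infections, using the same episode rule as incidence. State whether that rule runs pooled or by infection type. Restrict the row to patients with at least two such episodes, and report it for the overall follow-up period only.

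The change needs new wording in Table 8 and no new data. Its price is that fewer patients contribute an interval and that recurrences shorter than the washout are excluded by construction. With a pooled rule, a window such as day 1 to day 8 can hold no interval, hence the limit to the overall period.

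If the sponsor prefers to keep the claim-based measure, the smaller change is to put claims into the row label and to state in Table 8 and in the results that it does not measure time between separate infections.
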